12.3.4. Columbia-Suicide Severity Rating Scale (C-SSRS)

The C-SSRS is a questionnaire developed by researchers at Columbia University to assess and track suicide risk and behavior. This scale is intended to be used by individuals who have received training in its administration. The questions contained in the Columbia-Suicide Severity Rating Scale are suggested probes. Ultimately, the determination of the presence of suicidal ideation or behavior depends on the judgment of the individual administering the scale.

Two versions of this questionnaire will be utilized in this study. At Visit 1, the "Baseline/Screening" questionnaire will be administered, and the recall periods will be "lifetime" and "within the past 6 months" for suicidal ideation and "within the past 1 year" for suicidal behavior. Patients whose responses are indicative of suicidal ideation with intent and/or plan (e.g., Type 3, 4 or 5 suicidal ideation) within the past 6 months or a history of suicidal behavior within the past year will be excluded from participation, with recommended referral for appropriate intervention.

At all subsequent visits (Visits 2, 3, 4, 5 and 6), the "Since Last Visit" version of the questionnaire will be administered, and the recall period on this will be "since the last visit". Any significant increase in suicidal ideation noted should be documented and appropriate intervention prescribed.

12.3.5. Physical Examination and Vital Signs

A complete physical examination will be performed at Visit 1. The complete physical examination may exclude rectal, genitourinary, and breast examinations.

Vital signs (sitting blood pressure and heart rate, temperature, and weight) will be assessed at Visits 1, 2, 3, 4, 5 and 6 (unless a telephone visit, in which case vital signs will not be assessed at Visits 3, 4, 5, and 6/ET). Height will be measured without shoes at Visit 1 only. The BMI will

be a derived variable, based on height and weight entries (but a Week 14/ET weight will not be assessed, if approved by the Medical Monitor for a telephone visit).

12.3.6. Visual Examination of the Oral Cavity

A thorough examination (visual plus palpation) of the oral cavity will be completed at Visit 1, with visual examinations performed at each subsequent study visit (Visits 2, 3, 4, 5 and 6/ET). Visual exam of the oral cavity will not be performed if it is a telephone visit. This examination should include a careful visual examination of the sublingual area, tongue, buccal mucosa, lips, palate and gums, aided with a tongue depressor, as well as palpation of the lips, hard palate, and floor of the mouth.

Each examination must be performed by a qualified medical professional who has been specifically trained and certified by the Sponsor for this examination. An oral cavity examination may also be required at an unscheduled visit if a patient reports an oral AE that requires follow-up prior to the next scheduled visit.

12.3.7. Clinical Laboratory Assessments

The clinical laboratory evaluations to be performed in this trial are listed in Table 3. Those marked as screening tests will be performed at Screening only. All other tests will be performed at Screening Visit 1 and at Visit 6 (Week 14) or Early Termination, aside from urine pregnancy tests and ad hoc urine drug screens.

With the exception of the urine pregnancy test or an ad hoc urine drug screen, all clinical laboratory evaluations will be analyzed via a central clinical laboratory, and information regarding appropriate sample volume, collection tubes, sample labeling and handling, and shipment will be provided in the clinical laboratory manual.

As per exclusion criterion #14, any patient with evidence during the preceding year of drug or alcohol use disorder by MINI or history is ineligible.

A centrally analyzed urine drug screen (UDS) will be performed at Visit 1. If the patient has a positive drug screen at Visit 1 due to a drug of abuse (e.g., cocaine, methamphetamine, ecstasy) or due to a non-disclosed opioid, amphetamine or benzodiazepine, then he/she should be screen failed. As discussed in Section 9.2, patients utilizing cannabis/THC are to be excluded if MINI criteria are met for greater than MILD Cannabis Use Disorder during the preceding 12 months, OR if the investigator is concerned that the patient's use of cannabis/THC could interfere with patient's ability to provide reliable data or comply with the protocol. Otherwise, patients utilizing cannabis or THC products are allowed, with caution.

The screening drug screen will test for THC to provide the investigator with information regarding exposure, and to ensure that all usage is disclosed and taken into consideration when conducting MINI Module J. Repeat testing of THC is not necessary for patients testing positive for cannabis/THC at screening.

Any patient deemed appropriate for washout of a prescription opioid, benzodiazepine or amphetamine will require a repeat UDS before the beginning of their 7 days of baseline data collection leading up to Visit 2, the results of which must be negative and available for review

before randomization may occur. Therefore, these patients will need to return for an unscheduled visit after the first 2 weeks of washout have been completed. All benzodiazepine drug screening must be sent to the central laboratory for analysis, hence results may be delayed; all other repeat urine drug screening may be conducted on-site. Patients do not have to wait for confirmation of negative centralized benzodiazepine results before starting their 7-day baseline data collection phase, but all results must be confirmed negative prior to randomization.

Patients with a positive screening UDS due to an allowed prescription drug (e.g., headache remedies containing butalbital) do not require further drug screening.

Each clinically significant abnormal laboratory value or other clinically meaningful abnormality should be followed until the abnormality resolves or until a decision is made that it is not likely to resolve. If such abnormalities do not return to normal within a reasonable period, their etiology should be identified and Tonix or designee should be notified. Clinically significant abnormalities in laboratory values after the Screening visit labs will be recorded as AEs.

NOTE: A screening TSH level greater than 1.5 times higher than the upper limit of normal, or ALT or AST level > 2 times the upper limit of normal, is exclusionary; however, the patient may remain in screening to undergo repeat LFT assessments if a transient abnormality (eg, viral illness; effects of a medication being discontinued, etc) is thought to be responsible for their initial elevation.

Table 3: Clinical Laboratory Assessments

Clinical chemistry	Hematology
Alanine aminotransferase (ALT/SGPT) ^a	Hematocrit
Alkaline phosphatase	Hemoglobin
Aspartate aminotransferase (AST/SGOT) ^a	MCH concentration (MCHC)
Bicarbonate	Mean corpuscular hemoglobin (MCH)
Bilirubin (direct and total)	Mean corpuscular volume (MCV)
Blood urea nitrogen (BUN)	Platelet count
Calcium	Red blood cell (RBC) count
Chloride	WBC differential
Cholesterol (total)	Neutrophil count (absolute and %)
Creatine kinase (CK)	Lymphocyte count (absolute and %)
Creatinine	Monocyte count (absolute and %)
Glucose	Eosinophil count (absolute and %)
LDH	Basophil count (absolute and %)
Phosphorus	White blood cell (WBC) count
Potassium	Red blood cell distribution width (RDW)
Protein (albumin and total)	
Sodium	
HbA1c only if glucose > 180 mg/dL	
Thyroid-stimulating hormone (TSH) ^c at	Serum Pregnancy Test at Screening ^b
screening	
Free T4 only if TSH is outside of normal limits	Urine Pregnancy Test (qualitative dipstick) ^b
Pharmacogenomic testing (optional; can be	Urine Drug Screen ^d
obtained at any visit post-Screening, including	
an Early Termination visit)	

^a Level greater than 2 times the upper limit of normal is an exclusion (if persistent upon repeat).

12.3.8. Pharmacogenomics Testing

For pharmacogenomic analysis, a single blood draw of up to 20 mL will be obtained from each patient after they have provided separate written, signed informed consent for pharmacogenomic analysis. Due to circumstances caused by the COVID-19 pandemic and possibility of no further in-clinic visits after the Baseline visit (Visit 2), it is strongly recommended that the pharmacogenomics blood sample be obtained at the Baseline visit (Visit 2). The purpose of this testing is to allow genotyping for genetic variants related to treatment response to TNX-102 SL. It is presumed that unused extracted DNA sample will be stored up to fifteen years, and potentially utilized to develop a pharmacogenomic test for predicting treatment response to TNX-102 SL. A decision not to participate in optional pharmacogenomic testing will not affect the patient's eligibility for the main study. Patients have the right to stop participating at any time during the study or during the time of sample storage, and, if a patient decides to withdraw from the pharmacogenomics portion of this study, any remaining sample will be destroyed and not used for further research. Data collected before a patient's withdrawal from the pharmacogenomics portion of this study will remain in the research database and included in the sponsor's analyses and reports.

b Pregnancy testing for females of child-bearing potential only. A positive pregnancy test is exclusionary (Visit 1 or Visit 2) or mandates withdrawal from the study (all other visits).

^c TSH level greater than 1.5 times higher than the upper limit of normal is exclusionary at Visit 1.

^d Urine drug screening will be conducted on all patients at Screening and, if necessary, prior to the beginning of the 7-day baseline data collection phase in patients washing off opioids, amphetamines, or benzodiazepines and who otherwise qualify for the study.

13. STATISTICAL CONSIDERATIONS AND ANALYSES

A complete description of the statistical analyses to be performed will be provided in the study-specific SAP, which will be finalized prior to database lock and the unblinding of study treatments.

Baseline will be defined as those values recorded closest to, but prior to administration of the first dose of study drug.

Unless otherwise noted, significance tests of treatment differences will be tested at the two-sided 0.05 level.

13.1. Populations for Analysis

The following analysis populations are planned for this study:

- All subjects: Used for summaries of dispositions of patients; tabulations of dispositions may also use the populations below.
- Safety population: all patients who receive at least one dose of the investigational product. All safety analyses will be performed using this population, analyzed as treated.
- Intention-to-Treat (ITT) population: all patients who are randomized. This is the primary population for efficacy analyses, and patients will be analyzed based on their randomized treatment.

13.2. Estimate of Sample Size

This study is planned to enroll approximately 470 patients total in a 1:1 randomization, that is, 235 patients in each of the TNX-102 SL 5.6 mg and placebo arms.

13.3. Assessment of Demographic and Baseline Characteristics

Demographic and baseline characteristics such as age, gender, race/ethnicity, height, weight, BMI, family status, education, employment status, smoking history, MINI modules (A, C, I, J, K) diagnoses, and 2016 Revised 2010/2011 FM Diagnostic criteria will be summarized by treatment group (TNX-102 SL and placebo) and overall using descriptive statistics.

Medical History will be coded using the Medical Dictionary for Regulatory Activities (MedDRA)[®] and summarized by System Organ Class (SOC) and Preferred Term using frequency counts by treatment group.

13.4. Efficacy Analyses

13.4.1. Efficacy Endpoints

Primary Efficacy Endpoint:

• Change from Baseline to the Week 14 endpoint in the diary NRS weekly average of daily self-reported average pain severity scores.

Secondary Efficacy Endpoints:

The six secondary efficacy endpoints listed below are considered key secondary endpoints and will be tested in that order:

- Proportion of patients with a PGIC rating of "very much improved" or "much improved" at the Week 14 endpoint
- Change from baseline in the FIQR symptoms domain score at the Week 14 endpoint
- Change from baseline in the FIQR function domain score at the Week 14 endpoint
- Change from baseline in the PROMIS score for sleep disturbance at the Week 14 endpoint
- Change from baseline in the PROMIS score for fatigue at the Week 14 endpoint
- Change from baseline in the weekly average of the daily diary assessment of sleep quality at the Week 14 endpoint

Exploratory efficacy endpoints:

- Change from baseline in the in-clinic assessment of pain 24-hour recall
- Change from baseline in the in-clinic assessment of pain weekly recall
- Proportion of patients with a ≥30% improvement from baseline to Weeks 1-14 in the daily self-reported average pain severity score
- Proportion of patients with a ≥50% improvement from baseline to Weeks 1-14 in the daily self-reported average pain severity scores
- Proportion of patients with a PGIC rating of "very much improved" or "much improved" at all post-randomization clinic visits
- Proportion of patients with a PGIC rating of "minimally improved," "much improved," or "very much improved") at all post-randomization clinic visits
- Change from baseline in the FIQR total score, overall impact domain score, and individual item scores at all post-randomization clinic visits
- Change from baseline in the FIQR symptoms domain score and function domain scores at all post-randomization clinic visits
- Change from baseline in the PROMIS score for sleep disturbance at all postrandomization clinic visits
- Change from baseline in the PROMIS score for fatigue at all post-randomization clinic visits

- Change from baseline in the weekly average of the daily diary assessment of sleep quality at Weeks 1-14
- Change from baseline in the weekly average of the daily self-reported average pain severity scores at Weeks 1-14
- Changes from baseline in patient-rated Changes in Sexual Functioning Questionnaire Short-Form (CSFQ-14) in females and in males, analyzed separately

13.4.2. Primary Efficacy Analysis

The primary efficacy parameter will be the contrast between active and placebo in the weekly mean change from baseline pain score at the Week 14 endpoint. The weekly pain score will be based on the weekly average of the daily patient self-reported 24-hour recall average pain severity scores using an 11-point (0-10) NRS.

The primary ITT analysis will provide an estimate of the following causal estimand for the primary analysis: the difference in the weekly mean change from Baseline of the daily patient self-reported 24-hour recall average pain severity rating using an 11-point (0-10) NRS evaluated at the Week 14 endpoint in all randomized patients attributable to the initially randomized treatment assignment.

The primary analysis will use a MMRM approach with multiple imputation for missing data. Covariates in the model will include the fixed categorical effects of treatment, center, study week, and treatment by study week interaction, as well as the continuous fixed covariates of baseline score and baseline score by study week interaction. Please see the separate SAP for more details on the primary and secondary analyses.

13.4.3. Sensitivity Analyses

The primary analysis will be followed by several sensitivity analyses. The SAP will include full details of the sensitivity analyses planned for this study.

13.4.4. Secondary Efficacy Analyses

Secondary efficacy analyses will be based on the ITT population only. For PGIC, patients with a "very much improved" or "much improved" response at the Week 14 endpoint will be considered responders. Patients with results in any other category or who discontinue early will be considered non-responders. A categorical analysis of PGIC responder status (yes/no) will compare the treatment arms with a difference in proportions Z test (equivalent to a Pearson's Chi Squared). The percentages of responders and the 95% CIs of the percentages as well as the difference in the percentages and its 95% CI will be reported.

Analysis of continuous secondary endpoints and adjustments for missing data will be described in detail in the SAP. Significance tests of treatment differences will be tested at the two-sided 0.05 level and corresponding 95% confidence intervals will be calculated.

To adjust for multiplicity and to control for overall type I error, a sequential test procedure will be applied to the efficacy endpoints. If the primary analysis produces a result that is statistically significant at the 0.05 level, a significance level of 0.05 will be used for comparing the secondary endpoints in an ordered fashion. If the analysis for a secondary endpoint does not produce a statistically significant result at the 0.05 level, then the remaining secondary endpoint analyses

will automatically be considered non-significant regardless of the p-value produced. The order in which the secondary endpoints are to be tested will be specified in the SAP.

No other adjustments for multiplicity will be made and other p-values displayed in the output will be considered for descriptive summary purposes only and will not be used for formal inference. Full details regarding the statistical analyses for the listed endpoints, including graphical presentations, can be found in the SAP.

13.4.5. Exploratory Efficacy Analyses

Exploratory efficacy analyses will be based on the ITT population. Details on exploratory efficacy analyses can be found in the SAP.

13.5. Safety Analyses

Safety analyses will be performed using the Safety Population. The analysis of safety assessments in this study will include summaries of the following safety and tolerability data collected for each patient:

- Incidence of Adverse Events
- Changes from baseline in clinical laboratory tests
- Changes from baseline in vital signs
- Changes from baseline in physical examination findings including examination of the oral cavity
- Monitoring suicidality using the C-SSRS
- Changes from baseline in BDI-II scores

All AEs, treatment-emergent adverse events (TEAE), and serious adverse events (SAE) will be coded using the MedDRA.

An AE summary table will be presented for the following:

- All TEAEs
- TEAEs by severity
- TEAEs leading to study drug discontinuation
- TEAEs by relationship
- SAEs
- Oral cavity TEAEs
- Oral cavity TEAEs by severity

Summaries of incidence rates (frequencies and percentages), of individual AEs by MedDRA SOC and preferred term will be prepared. Such summaries will be displayed for all TEAEs, oral cavity TEAEs, TEAEs by maximum severity, and TEAEs by strongest relationship to study drug.

Each patient will be counted only once within each summation level (SOC; preferred term). If a patient experiences more than one TEAE within each summation level, the TEAE with the strongest relationship or the maximum severity, as appropriate, will be included in the summaries of relationship and severity.

In the AE data listings, all AEs will be displayed.

Laboratory data include analytes for Chemistry and Hematology, and these will be summarized by treatment and visit for the Safety Population. Descriptive summaries of actual values and changes from baseline will be presented by study visit and last on-treatment assessment for each clinical laboratory analyte and each treatment group. 95% confidence intervals will be presented for change from baseline.

Laboratory values will be displayed in the data listings with their corresponding normal ranges, and those values that are outside the normal range will be flagged. For each laboratory analyte, shifts in assessments of abnormality from baseline to each scheduled time point will be presented in shift tables.

A by-patient listing of all clinical laboratory data will also be provided.

Descriptive summaries (mean, SD, median, minimum, and maximum) of actual values and changes from baseline at each assessment time point and last on-treatment assessment will be calculated for vital signs including weight, BMI, body temperature, pulse rate, systolic blood pressure and diastolic blood pressure. 95% confidence intervals will be presented for change from baseline.

Based on the C-SSRS results, the overall number of patients with lifetime and/or current suicidal ideation (by item and category), suicidal behavior (by item and category), or self-injurious behavior at the screening and baseline visit will be summarized by visit and treatment group. Additionally, the overall number of patients with any suicidal ideation or behavior (by type and in total) or self-injurious behavior while on-treatment will be provided by treatment group. Patients will only be counted once for on-treatment at the worst-case response for each item.

Physical examination data and oral examination data will be presented in data listings.

Descriptive summaries (mean, SD, median, minimum, and maximum) of actual values and changes from baseline at each assessment time point and last on-treatment assessment will be calculated for BDI-II scores. 95% confidence intervals will be presented for change from baseline.

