12.3.3. Beck Depression Inventory (BDI-II)

The BDI-II is a 21-item measure of the severity of current depressive symptoms, extensively validated for use in both medical and mental health populations. While this instrument does not provide a psychiatric diagnosis of depression, it does provide a continuous scale for measuring the severity of depressive symptomatology. Scoring allows for the identification of mild, moderate, and severe levels of depressive symptoms, and for the quantification of change in status over time.

The patient will be asked to complete this questionnaire at all in-clinic study visits, and for all telephone visits. The BDI-II will be sent by courier to the patient in advance of the phone call. At Visit 1 and Visit 2, patients whose responses are indicative of suicidal ideation, as defined by a response to Item #9 of >1, will be excluded from participation, and appropriate intervention prescribed. In addition, patients whose total BDI score is > 24 at either Visit 1 or Visit 2 will not be eligible for randomization and should be screen failed (and referred for appropriate psychological evaluation or care, if indicated). After Visit 1, the responses to Question #9 should be monitored to ensure that there is no increase in suicidal ideation during the study (and to assess correlation with C-SSRS findings) and the total score also followed to ensure the patient's psychological status remains stable.

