8. GENERAL ISSUES FOR STATISTICAL ANALYSIS

8.1 General Statistical Methodology

Descriptive summaries will be provided where appropriate for each of the primary and secondary variables. In general, tables will summarize data by treatment group and visit. All patients for a population in each treatment group will be grouped together; patients that reduce dose from two tablets per day to one tablet per day will be not be reported separately for the analyses described in this SAP, unless otherwise noted. If there are more than 10% of patients in the active arm with a dose reduction at any point in the study, summary statistics on key outcomes may be reported for patients with dose reductions.

Baseline characteristic and safety tables will be completed for the Safety Population unless otherwise specified. Efficacy tables will be presented for the ITT Population.

Continuous, quantitative variable summaries will include the number of patients (N) with non-missing values, mean, standard deviation, median, minimum, and maximum.

Categorical, qualitative variable summaries will include the frequency and percentage of patients who are in the particular category. In general, the denominator for the percentage calculation will be based upon the total number of patients in the study population for the treatment group unless otherwise specified.

Baseline values are defined as the last non-missing measurement prior to the first dose of study drug. For scores obtained via diary, baseline will be defined as the average of the scores from the 7 days prior to the baseline visit. Change from baseline will be defined as the post-baseline visit value minus the baseline value.

Study day is defined as assessment date – first dose date +1 for dates on/after first dose date and assessment date – first dose date for those before.

All analyses will be performed using SAS® Software version 9.4 or later.

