11.4 Beck Depression Inventory II

Descriptive summaries (mean, SD, median, minimum, and maximum) of actual values and changes from baseline at each assessment time point and last available assessment will be calculated for the BDI-II total score. 95% confidence intervals will be presented for change from baseline.

These summaries will be presented by treatment and assessment time for the Safety population. ET data will be analyzed with the closest visit that does not have a valid assessment value.

Protocol: TNX-CY-F307 Page 34 of 45

Final v1.0

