11.5 Vital Signs

Descriptive summaries (mean, SD, median, minimum, and maximum) of actual values and changes from baseline at each assessment time point and last available assessment will be calculated for vital signs including weight, BMI, body temperature, pulse rate, systolic blood pressure and diastolic blood pressure. 95% confidence intervals will be presented for change from baseline.

These summaries will be presented by treatment and assessment time for the Safety population. ET data will be analyzed with the closest visit that does not have a valid assessment value.

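### Laboratory values, vital signs and BDI-II get 95% confidence intervals only for change within each arm; no TNX-102 SL minus placebo difference is planned

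*Protocol*

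**What the plan says.** Protocol 13.5 plans descriptive summaries of actual values and changes from baseline, with an interval, for three kinds of continuous safety data:

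- Laboratory values are summarised "for each clinical laboratory analyte and each treatment group. 95% confidence intervals will be presented for change from baseline". SAP 11.2 repeats this.
- For vital signs, the list of measures ends "systolic blood pressure and diastolic blood pressure. 95% confidence intervals will be presented for change from baseline". SAP 11.5 repeats the interval and adds: "These summaries will be presented by treatment and assessment time for the Safety population".
- BDI-II follows the same pattern in Protocol 13.5, where the summaries "will be calculated for BDI-II scores. 95% confidence intervals will be presented for change from baseline". SAP 11.4 repeats it: "95% confidence intervals will be presented for change from baseline".

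The layout rule in SAP 8.1 is: "In general, tables will summarize data by treatment group and visit". Only the laboratory text names the treatment group in the sentence just before the interval. For vital signs and BDI-II, the within-arm reading follows from the table layout.

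Elsewhere the plan does compare arms. PGIC gets a difference in percentages with its 95% interval (Protocol 13.4.4; SAP 10.2). CSFQ-14, which SAP 10.3 treats as supportive of safety and SAP 11 lists among the safety data, gets an ANCOVA with treatment, pooled site and baseline.

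**The concern.** Safety is the secondary objective of a placebo-controlled trial, and the comparison that randomization supports is between arms. A within-arm interval answers a different question: did this arm's mean move from its own baseline? That movement combines any drug effect with whatever would have happened anyway.

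The documents contain features that could produce such shared movement. On BDI-II, "patients whose total BDI score is > 24 at either Visit 1 or Visit 2 will not be eligible for randomization". A cap on the qualifying values tends, taken alone, to make later values drift upward. ALT or AST above 2 x ULN is exclusionary (Protocol 8.3 and 12.3.7), which has the same tendency where the screening value serves as baseline. Time trends over 14 weeks, including general improvement in a trial, can act on any measure and in either direction.

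Two misreadings become possible. An active-arm interval that excludes zero may be taken for a drug effect when it reflects shared change. A real drug effect may be hidden when the shared change runs the other way. Setting the two arms' intervals side by side and noting which excludes zero solves neither, because that is not a valid comparison of arms.

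**Working it through.** **Inputs from the documents.** 235 patients per arm (Protocol 13.2; SAP 6); 2 x 235 = 470 agrees with the stated total. Intervals are at 95%. The documents give no SD, expected change or effect size for any safety measure, so there is no planned figure for these intervals to reproduce. The sizes below are assumptions, in units of the SD of the change score.

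**1. Width.**
- Within-arm half-width: 1.96/√235 = 0.128 SD.
- Unadjusted between-arm half-width: 1.96 x √(2/235) = 0.181 SD.
- Ratio: √2 = 1.41. The within-arm interval looks more precise because it omits the placebo arm's variability.

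**2. No drug effect, shared change m.** The probability that one arm's interval excludes zero is p = Φ(m√n − 1.96) + Φ(−m√n − 1.96). For m = 0.1, m√235 = 1.533, so p = Φ(−0.427) + Φ(−3.493) = 0.335.

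| Shared change (SD) | Active-arm interval excludes 0 | Exactly one arm's interval excludes 0, 2p(1−p) | Between-arm interval excludes 0 |
|---|---|---|---|
| 0 | 5% | 9.5% | 5% |
| 0.05 | 12% | 21% | 5% |
| 0.1 | 33% | 45% | 5% |
| 0.2 | 87% | 23% | 5% |
| 0.3 | 99.6% | 0.8% | 5% |

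The last column is constant because a change equal in both arms cancels in the difference.

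**3. Masking.** Suppose both arms would improve by some amount and the drug worsens the measure by the same amount. The active arm's mean change is then zero, and its interval excludes zero in 5% of trials. The between-arm interval excludes zero with probability Φ(d/√(2/235) − 1.96):
- d = 0.2 SD: Φ(2.168 − 1.96) = 58%.
- d = 0.3 SD: Φ(3.252 − 1.96) = 90%.

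**4. Fewer evaluable patients.** With 188 per arm (an assumed 20% loss), the active-arm figures with no drug effect are 28% at 0.1 SD and 78% at 0.2 SD. The between-arm figure for a 0.3 SD effect is 83%.

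**5. How large could the shared change be on BDI-II?** Assume normal scores with SD 9, a screened-population mean of 10 to 18 and a between-visit correlation of 0.6 to 0.9, with entry at or below 24 at both visits. None of these inputs is in the documents. Simulation gives an upward drift from the cap alone of 0.1 to 1.2 points. Each arm's interval would then exclude zero in 6% to 63% of trials with no drug effect. The top of that range needs a mean of 18 and a correlation of 0.6, where about 37% of screened patients would fail on BDI-II alone. Mid-range (mean 14, correlation 0.75), the drift is about 0.4 points and the rate about one trial in six. A shared on-study improvement of 0.5 points brings that rate down to about 6%; a larger improvement reverses the sign.

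**The case against.** The strongest reply is that these are descriptive summaries. No test, threshold or conclusion depends on the intervals, and placebo sits beside active in the tables. SAP 8.1 specifies n, mean and SD, so a reader can derive an unadjusted difference and its interval. Laboratory data also get shift tables and out-of-range flags, and adverse events and C-SSRS results are shown by arm. All of this stands. It limits the point to which interval is displayed. It does not explain why the one interval shown should be the one that cannot separate drug effect from shared change.

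A reader might also infer stronger things that the documents do not support:

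- **That the plan judges drug effects against zero.** Zero is what a within-arm interval refers to, but no rule to that effect is written.
- **That BDI-II is bound to drift upward.** The cap pushes that way, but its size is unknown and on-study improvement could offset or reverse it.
- **That the laboratory baseline always precedes washout.** Protocol 12.3.7 says "All other tests will be performed at Screening Visit 1 and at Visit 6 (Week 14) or Early Termination". But Table 2 carries a second screening entry for laboratory tests, tied to a footnote describing an unscheduled visit during washout. Section 12.3.7 also allows repeat liver tests, and SAP 8.1 takes the last non-missing value before first dose. Washout concerns only patients on excluded drugs.
- **That vital signs have a built-in drift.** No entry limit on pulse, blood pressure or temperature is stated, and vital signs are re-measured at Visit 2. Only general time trends apply.
- **That 9.5% discordance exceeds a permitted 5%.** These are different events; no 5% rate was ever set for two arms' intervals disagreeing.

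Finally, cancellation is not guaranteed in every summary. The last-observation summary in SAP 8.1.2 pools early-termination visits at any time with Week 14, so differing dropout could leave shared change uncancelled. That qualifies the remedy for that summary.

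**Conclusion.** The point holds in limited form. For laboratory values, vital signs and BDI-II, both documents plan an interval for each arm's own change and none for the difference between arms. This is a less informative choice in a placebo-controlled trial whose secondary objective is safety. It is not an invalid test, and no planned conclusion rests on it.

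The size depends on a shared change that the documents do not state. The false-signal and masking figures illustrate what within-arm intervals can do at assumed values; they do not predict this trial. They assume 235 evaluable patients per arm, approximately normal means, equal SDs and a shared change that is the same in both arms. The case has most document support for BDI-II and the liver enzymes, because of their entry caps, and least for vital signs.

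**What to change.** In Protocol 13.5 and SAP 11.2, 11.4 and 11.5, keep the per-arm descriptive statistics and add the TNX-102 SL minus placebo difference in change from baseline, with a 95% interval labelled descriptive. Take it from an ANCOVA with treatment and the baseline value of the measure. Report it at Week 14. Report it also for the last-assessment summary, with a note that the timing of early-termination visits may differ by arm.

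The cost is SAP wording and one extra column per table. No new data, sample size or alpha change is needed, and the SAP already uses an ANCOVA for CSFQ-14. The downside is more intervals across many analytes, unadjusted for multiplicity, so some will exclude zero by chance. The label should say so.
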